Eligible patients were 18 years of age and older who have an ECOG performance status, 0-2; and adequate organ function with histologically proven malignant solid tumors who were receiving their second, third, or fourth line of palliative chemotherapy and who showed – at the second or third chemotherapy course – progressive disease as their maximum response according to Response Evaluation Criteria in Solid Tumors (RECIST), or Gynecologic Cancer Intergroup (GICG) CA125 criteria in the case of patients with ovarian cancer. **Schedules comprised cisplatin; carboplatin; paclitaxel; vinorelbine; gemcitabine; pemetrexed; topotecan; doxorubicin; cyclophosphamide, and anastrozole.** A total of 17 patients whose primary tumors sites were cervix (3), breast (3), lung (1), testis (1), and ovarian (7) carcinomas, were evaluable for toxicity, and 15 for response. Most patients were heavily treated, and had received two and three previous lines of treatment. After entering the protocol, of note, patients re-started the schedule employing the same dose they received previously. Clinical benefit (complete or partial response and disease stabilization) was observed in 12 (80%) of the 15 patients; four partial and eight stabilization of disease. Among partial responses, three were in ovarian cancer according to IGCG CA125 criteria, and a PR was observed in one patient with cervical cancer by MRI of a supraclavicular lymph node disease. Regarding patients with stable disease, four occurred in patients with ovarian cancer and one each in patients with cervix, lung, testis, and breast. The majority of patients who exhibited response or stabilization also demonstrated improvement in symptoms such as dyspnea, cough, and pain. Regarding evaluation of response according to total number of evaluable disease sites, there were 16 evaluable lesions in the eight cases excluding ovarian malignancies. Of these, one (6.6%) complete and three (18.75%) partial responses were achieved, whereas nine (56.2%) had disease stabilization. The treatment was well tolerated despite the study population was heavily pre-treated. The median number of weeks that patients received protocol therapy was 9.5 (range, 6–17 weeks) and the most significant toxicity was hematological. This hematological toxicity led to a decrease in dose intensity in nine (60%) patients as compared to that previous to entering the protocol. Non-hematological toxicity, that could be attributed to valproate consisted on grade 3 drowsiness in three and delirium in one patient, respectively. These antitumor effects resulted in a median progression-free survival of 3.3 months (range 2.4–5.7 months) and median survival was 6.1 months (range 3.8–12.8 months). Regarding pharmacodynamic endpoints, there was a mean reduction of 23.3% in HDAC activity at

day 8 of treatment with the epigenetic agents. These effects were seen at a mean concentration of 86.3 μ g/mL of VPA levels in plasma. This study was not intended to have post-treatment samples of tumors, instead, the promoter methylation of three genes (*hMLH*, *RAR α* , and *DAPK*) were analyzed from serum DNA. Overall, of 15 informative methylation-specific PCR, reactions five (33.3%) showed promoter demethylation. As for patients, eight of nine were informative and four (50%) had demethylation of at least one gene. These results suggest that the response and disease stabilization rates observed with valproate and hydralazine may have resulted from the overcoming of epigenetic changes, mediating chemotherapy resistance (62).

In the most recent phase II study which is submitted to publication, the combination of valproate and hydralazine was added to standard cisplatin chemoradiation in FIGO stage IIIB patients under the rational that these drugs in combination show inhibitory growth effect *in vitro* and *in vivo*, chemosensitization, a synergistic effect upon global gene expression (36), and up-regulation of Human leukocyte antigen (HLA) class I antigen expression and antigen-specific Cytotoxic T-lymphocyte (CTL) response in cervical cancer cells without increasing human papillomavirus oncogene expression (63). Moreover, cervical cancer exhibits a number of cellular epigenetic alterations that include abnormal activity of DNMT1 and HDAC1 proteins, which are targets of the E7 oncoprotein during the HPV transformation process (64).

In this study, eligible patients were patients with cervical cancer staged as IIIB, aged more than 18 years, with an ECOG performance status, 0-2; and adequate organ function. Treatment included the combination of valproate hydralazine as above described starting 7 days before weekly cisplatin at 40 mg/m² and external and intracavitary pelvic radiation. The results demonstrate that out of 18 patients evaluable for response, all have a clinical complete response at the end of external radiation and no side effects other than increased but manageable myelotoxicity in addition to grade 3 asthenia (9%), nausea/vomiting (14%), diarrhea (9%), proctitis (9%), hypoalbuminemia (9%), and headache (5%). Somnolence was observed in 73% of patients, but it was grades 1 and 2. Interestingly, a comparison between pre- and post-treatment biopsies (after the seven days of treatment with valproate and hydralazine) showed moderate-to-intense infiltration of tumor and stroma, composed mainly of lymphocytes as well as an increase in connective tissue with fragmentation of solid malignant nests, with a trabecular pattern, indicating that these drugs exert by their own a modest antitumor effect. The mean concentrations in plasma of VPA at weeks 1, 4 and 7 were 66.4, 63.7, and 63.5 μ g/mL, respectively, for an overall mean of 64.5 μ g/mL. Interestingly, in this study, 10 pairs of tumor samples before and after valproate hydralazine could be analyzed for global gene expression by microarray analysis. There were 964 significant up-regulated genes with a false discovery rate <5%. (GEO Submissions GSE8604)."

1.2.2 Safety Profile for VPA

Frequency of adverse effects by organ system:

>10%:

Central nervous system: Headache (>31%), somnolence (>30%), dizziness (12% to 25%), insomnia (>1% to 15%), nervousness (>1% to 11%), pain (1% to 11%)

Dermatologic: Alopecia (>1% to 24%)

Gastrointestinal: Nausea (15% to 48%), vomiting (7% to 27%), diarrhea (7% to 23%), abdominal pain (7% to 23%), dyspepsia (7% to 23%), anorexia (>1% to 12%)

Hematologic: Thrombocytopenia (1% to 24%; dose related)

Neuromuscular & skeletal: Tremor (>57%), weakness (6% to 27%)

Ocular: Diplopia (>1% to 16%), amblyopia/blurred vision (>12%)

Miscellaneous: Infection (>20%), flu-like syndrome (12%)

1% to 10%:

Cardiovascular: Peripheral edema (>1% to 8%), chest pain (>1% to <5%), edema (>1% to <5%), facial edema (>1% to <5%), hypertension (>1% to <5%), hypotension (>1% to <5%), palpitation (>1% to <5%), postural hypotension (>1% to <5%), tachycardia (>1% to <5%), vasodilation (>1% to <5%), arrhythmia

Central nervous system: Ataxia (>1% to 8%), amnesia (>1% to 7%), emotional lability (>1% to 6%), fever (>1% to 6%), abnormal thinking (>6%), depression (>1% to 5%), abnormal dreams (>1% to <5%), agitation (>1% to <5%), anxiety (>1% to <5%), catatonia (>1% to <5%), chills (>1% to <5%), confusion (>1% to <5%), coordination abnormal (>1% to <5%), hallucination (>1% to <5%), malaise (>1% to <5%), personality disorder (>1% to <5%), speech disorder (>1% to <5%), tardive dyskinesia (>1% to <5%), vertigo (>1% to <5%), euphoria (1%), hypoesthesia (1%)

Dermatologic: Rash (>1% to 6%), bruising (>1% to 5%), discoid lupus erythematosus (>1% to <5%), dry skin (>1% to <5%), furunculosis (>1% to <5%), petechia (>1% to <5%), pruritus (>1% to <5%), seborrhea (>1% to <5%)

Endocrine & metabolic: Amenorrhea (>1% to <5%), dysmenorrhea (>1% to <5%), metrorrhagia (>1% to <5%), hypoproteinemia

Gastrointestinal: Weight gain (4% to 9%), weight loss (6%), appetite increased

(·6%), constipation (>1% to 5%), xerostomia (>1% to 5%), eructation (>1% to <5%), fecal incontinence (>1% to <5%), flatulence (>1% to <5%), gastroenteritis (>1% to <5%), glossitis (>1% to <5%), hematemesis (>1% to <5%), pancreatitis (>1% to <5%), periodontal abscess (>1% to <5%), stomatitis (>1% to <5%), taste perversion (>1% to <5%), dysphagia, gum hemorrhage, mouth ulceration

Genitourinary: Cystitis (>1% to 5%), dysuria (>1% to 5%), urinary frequency (>1% to <5%), urinary incontinence (>1% to <5%), vaginal hemorrhage (>1% to 5%), vaginitis (>1% to <5%)

Hepatic: ALT increased (>1% to <5%), AST increased (>1% to <5%)

Local: Injection site pain (3%), injection site reaction (2%), injection site inflammation (1%)

Neuromuscular & skeletal: Back pain (·8%), abnormal gait (>1% to <5%), arthralgia (>1% to <5%), arthrosis (>1% to <5%), dysarthria (>1% to <5%), hypertonia (>1% to <5%), hypokinesia (>1% to <5%), leg cramps (>1% to <5%), myalgia (>1% to <5%), myasthenia (>1% to <5%), neck pain (>1% to <5%), neck rigidity (>1% to <5%), paresthesia (>1% to <5%), reflex increased (>1% to <5%), twitching (>1% to <5%)

Ocular: Nystagmus (1% to 8%), dry eyes (>1% to 5%), eye pain (>1% to 5%), abnormal vision (>1% to <5%), conjunctivitis (>1% to <5%)

Otic: Tinnitus (1% to 7%), ear pain (>1% to 5%), deafness (>1% to <5%), otitis media (>1% to <5%)

Respiratory: Pharyngitis (2% to 8%), bronchitis (5%), rhinitis (>1% to 5%), dyspnea (1% to 5%), cough (>1% to <5%), epistaxis (>1% to <5%), pneumonia (>1% to <5%), sinusitis (>1% to <5%)

Miscellaneous: Diaphoresis (1%), hiccups

<1%, postmarketing, and/or case reports (limited to important and/or life-threatening):

Aggression, agranulocytosis, allergic reaction, anaphylaxis, anemia, aplastic anemia, asterixis, behavioral deterioration, bilirubin increased, bleeding time altered, bone marrow suppression, bone pain, bradycardia, breast enlargement, cutaneous vasculitis, carnitine decreased, cerebral atrophy (reversible), coma (rare), dementia, encephalopathy (rare), enuresis, eosinophilia, erythema multiforme, Fanconi-like syndrome (rare, in children), galactorrhea, hematoma formation, hemorrhage, hepatic failure, hepatotoxicity, hostility, hyperactivity, hyperammonemia, hyperammonemic encephalopathy (in patients with UCD), hyperglycinemia, hypersensitivity reactions (severe, with multiorgan dysfunction), hypofibrinogenemia,

hyponatremia, hypothermia, inappropriate ADH secretion, intermittent porphyria, LDH increased, leukopenia, lupus, lymphocytosis, macrocytosis, menstrual irregularities, pancytopenia, parkinsonism, parotid gland swelling, photosensitivity, platelet aggregation inhibited, polycystic ovary disease (rare), psychosis, seeing "spots before the eyes," Stevens-Johnson syndrome, suicidal behavior/ideation, thyroid function tests abnormal, toxic epidermal necrolysis (rare), urinary tract infection

BOX WARNINGS:

Hepatotoxicity

Potentially fatal hepatic failure can occur.

Usually occurs during the initial 6 months of therapy. Children <2 years of age are at considerably increased risk of developing fatal hepatotoxicity, especially those receiving multiple anticonvulsants and those with congenital metabolic disorders, severe seizure disorders accompanied by mental retardation, or organic brain disease. Above this age group, the risk of fatal hepatotoxicity decreases considerably in progressively older patient groups. Serious fatal hepatotoxicity may be preceded by symptoms such as malaise, weakness, lethargy, facial edema, anorexia, and vomiting.

Monitor patients closely for development of any such changes.

Perform liver function tests prior to and at frequent intervals during therapy, especially during the first 6 months.

Fetal/Neonatal Morbidity and Mortality

Can produce teratogenic effects (e.g., neural tube defects such as spinal bifida).

Use in women of childbearing potential requires that potential benefits of therapy be weighed against the risk of fetal injury.

Pancreatitis

Life-threatening pancreatitis has occurred both in children and adults. Some cases described as hemorrhagic with rapid progression from initial symptoms to death. Can occur shortly after initial use as well as after several years of use. Warn patients and caregivers that abdominal pain, nausea, vomiting, and/or anorexia can be symptoms of pancreatitis that require prompt medical evaluation.

Usually discontinue the drug and initiate alternative therapy if pancreatitis is diagnosed.

1.3 Rationale

On the basis of the results from the studies cited above, we hypothesize that VPA may decrease pleural effusion production in cancer patients by inducing quiescence in the tumor cells through a dedifferentiation mechanism. To test this hypothesis, we propose to treat breast cancer patients who need an indwelling pleural catheter due to malignant pleural effusion with 10 weeks of VPA and compare to those treated with placebo. This compound inhibits histone deacetylase, and has shown a relatively safe profile at a dose of 30 mg/kg/day divided into three doses even in combination with second and third line chemotherapy drugs. This dose is expected to lead to hyperacetylation of H3 and H4 in most patients. Successful results of this study may improve the symptom

burden of end stage cancer patients with recurrent pleural effusion, and may reduce the expenses associated with their disease.

2.0 Objectives

2.0 Study Objectives

2.1 Research Design and Methods

Our goal is to better understand the biology of breast cancer stem cells and pleural effusion formation to improve therapy of malignant pleural effusion in breast cancer patients. Based on our preclinical studies described in the background section, a clinical trial is planned to answer specific questions regarding the role of histone deacetylation and effect of its inhibition on breast patients with MPE. In this study, eligible patients with recurrent symptomatic MPE who need an indwelling pleural catheter based on MDACC algorithms for placement will have one placed and will receive 10 weeks of VPA or placebo.

The first aim is to achieve a beneficial clinical effect of VPA on patients with MPE. The specific question is if VPA alters pleural effusion re-accumulation following placement of an indwelling pleural catheter to the extent that it will enable significant shortening of time to removal of the catheter compared to placebo. Additional aims will analyze the biology of histone deacetylation inhibition in MPE and will help to develop biomarkers of activity and noninvasive monitoring to such therapy:

The second aim is to analyze the amount of daily fluid drained with therapy. Patients will be provided a daily fluid drainage diary.

The third aim is to assess radiographic and clinical correlates using standard of care testing and assessment: Chest x-ray and CT to study effect on primary tumor burden and assessment of overall survival.

Our fourth aim is to study biological correlates. We will study the level of H3 and h4 hyperacetylation and inflammatory cytokines in the effusion and in the serum at baseline and at week 2. Fluid will be collected and stored if applicable from visits at baseline, at week 2, 6, and 10. We plan to study expression of stem cell markers on cells from effusion to demonstrate inhibitory effect of VPA on these cells. Urine will be collected and stored if applicable at baseline, weeks 2, 6, and 10 for correlative studies. Finally, we will study the effect of VPA therapy on level of circulating tumor cells.

Our fifth aim is to assess drug effect on patient symptoms, dyspnea and exercise tolerance using the EuroQOL, St George's respiratory questionnare and six-minute walk test respectively.

2.2 Primary Objective

- 2.2.1 To examine the effect of VPA on the time between placement of an indwelling pleural catheter and its removal due to successful treatment of pleural effusion.

2.3 Secondary Objectives

- 2.3.1 Measure the amount of pleural fluid drainage.
- 2.3.2 Study expression of inflammatory cytokines using the Luminex platform and the degree of H3 and H4 hyperacetylation in serum and pleural effusion cells.
- 2.3.3 Evaluate the effect of the study agent on tumor burden with chest CTs.
- 2.3.4 Evaluate the effect of the study agent on symptom burden, dyspnea and exercise tolerance
- 2.2.5 Measure level of circulating tumor cells in peripheral blood and pleural effusion.
- 2.2.6 Study expression of cancer stem cell markers on tumor cells in pleural effusion.
- 2.2.7 Record treatment related toxicity.
- 2.2.8 Record overall survival
- 2.2.9 Obtain urine samples for correlative studies

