1.0 Background

1.0 Introduction

The intent of this protocol is to reduce the burden of pleural effusion in patients with metastatic breast cancer such that the time of indwelling catheter can be reduced. The hypothesis is that pleural effusion tumor burden is dictated by the amplification and expansion of progenitor cells that could be inhibited by pushing the stem/progenitor equilibrium back towards a more quiescent cancer stem cell using the histone deacetylase (HDAC) inhibitor, valproic acid (VPA). Patients who could benefit from an indwelling catheter based on MDACC algorithms for placement will be randomized to 10 weeks of valproic acid or placebo and a pleural catheter placed. Time to catheter removal based on MDACC algorithms will be the primary endpoint. Serial fluid samples will be examined to validate the translational hypothesis and ensure HDAC inhibition occurs.

[figure not shown]

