In an IRB-approved laboratory study we cultured pleural effusion cells as spheres in tumor-initiating culture conditions (17, 18) and completed fresh flow cytometry analysis of the percentage of CD44+CD24-/lo epithelial cells (detected as CD45-CD326+ CD44+CD24-/lo cells) from 29 unselected patients with metastatic breast cancer who underwent pleurocentesis for symptomatic pleural effusion (Figure 1). In this exploratory analysis, we retrospectively examined the association between TICs and overall survival from the time of pleurocentesis and report that patients with higher percentages of TICs in the pleural fluid had significantly shorter overall survival than those with fewer TICs.

We analyzed fresh MPE samples from 29 pts with breast cancer for epithelial cells with a tumor-initiating cell phenotype (TIC, CD45-CD326+ CD44+CD24-/lo): CD45- (leukocyte

marker), CD326+ (also known as EpCAM an epithelial marker), and CD44+ and CD24-/lo (tumor-initiating markers), using multicolor flow cytometry on an IRB-approved protocol. Overall survival (OS) was measured from time of MPE assessment. Univariate analyses of survival were performed using Cox proportional hazards (CPH), with 1-year levels computed using the method of Kaplan-Meier. Multivariate analyses were performed using the CPH model. Median follow-up was 4.1 months, range 0.2 to 28.9. Eighteen patients have died of disease. Median percentage of CD45-CD326+ cells was 1.24% which contained a median TIC component of 9.5%. On univariate analysis, higher level of %TICs were significantly associated with differences in overall survival (Figure 2, $P = 0.005$). Actuarial 1-yr OS was 24% vs. 77% for patients with %TIC above (TIChi) and below (TIClo) the median ($P = 0.016$). Increasing percentage of TICs remained a significant predictor for worse OS on multivariate analysis (hazard ratio 1.25, confidence interval 1.06-1.49, $P = 0.007$). An increased percentage of TICs predicted for decreased OS among patients with MPE consistent with the hypothesis that these cells mediate recurrence and death from breast cancer.

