In a phase II clinical trial of VPA and the breast cancer regimen FEC100 (5-fluorouracil, epirubicin, cyclophosphamide 7/8 breast cancer patients had stable disease or partial response(34). Cell culture and xenograft studies suggest a synergistic interaction between histone deacetylase inhibitors (HDACi) and topoisomerase (topo) inhibitors, as well as other DNA targeting agents. In this phase I/II study, Munster et al determined the effects of escalating doses of VPA on the clinical efficacy and tolerability of epirubicin. The phase I part was open to patients with all solid tumors. A limited phase II part at the maximum tolerated dose (MTD) of VPA enrolled 10 breast cancer patients and incorporated the breast cancer regimen FEC100 (600/100/600 mg/m²). VPA was given on days 1-3 prior to epirubicin/FEC100 in 3-week cycles. HDAC expression, histone acetylation and topo II expression were evaluated in pre-and post-VPA peripheral blood mononuclear cells and tumor samples. Fifty-four (44 in phase I and 10 in phase II) patients [median age 55 (39-78)] received VPA (mg/kg/day): 15, 30, 45, 60, 75, 90, 100, 120, 140 and 160. Tumor types included: breast (10+10), melanoma (11), lung (6), sarcoma (2), GYN (2), GI (5) and others (8). Dose-limiting toxicities included somnolence, confusion and febrile neutropenia. No exacerbation of FEC100/epirubicin-related toxicities was observed. Objective responses in the phase I part 9/41 (22%) were seen across different tumor types despite a median number of 3 (0-6) prior regimens with stable disease/minor response in 16/41 (39%). In the breast-specific phase II part, partial responses to date were seen in 4/8 (50%) and stable disease in 2/8 (25%), progression in 1/8 (12.5%), 1/8 (12.5%) patients withdrew consent. All breast cancer patients with a response/stable disease received the maximal number of seven cycles. VPA plasma concentrations correlated with VPA dose. There was a positive correlation between histone acetylation and VPA dose as well as plasma levels in PBMC and further correlated with those in tumors. A sequence-specific combination of VPA and FEC100 in breast cancer is highly active without exacerbation of chemotherapy-induced toxicities. A neoadjuvant phase II trial using VPA (120 mg/kg) -> FEC100 in patients with early stage breast cancer is ongoing.

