3.4 On-Study Evaluations

On the day of indwelling intrapleural catheter placement the patient's pleural fluid will be drained, recorded and sent for cytology review. On the day of indwelling intrapleural catheter placement patients will receive VPA or **placebo** if cytology is positive. Patients will be provided a diary to record drainage from home.

Patients will be treated for the whole period of 10 weeks, and clinical course of disease will be monitored throughout this time. (Note: evaluations may be done within \pm 7 business days of the date specified in the protocol).

Patients will initially receive daily oral VPA 15 mg/kg/day divided in three doses or placebo divided in three doses. Based on the patient's bmi, obese patient dosing will be based on the adjusted body weight calculated using the MD Anderson Clinical

Calculator Formula (<http://inside2.mdanderson.org/apps/calculators/calc1.cfm>). If the patient tolerates the reduced dose for 10 consecutive days then the VPA dose will increase to 30 mg/kg/day divided into three doses or placebo divided into three doses. The patient will be contacted by phone to assess tolerance and instruction to increase dose. Daily dose in mg will be divided by 250 mg and rounded down to a whole number of capsules to determine the number of VPA tablets or placebo tablets to be taken 3 times per day.

Evaluations may occur any time during weeks 2, 6, and 10.

- 3.4.1 Patients will document daily amount of pleural fluid drainage.
- 3.4.2 Patients will be evaluated at weeks 2, 6, and 10 with complete interim histories and physical examinations including measurement of vital signs, performance status, weight and medical history.
- 3.4.3 Patients will complete a EQ-5D and St. George's respiratory questionnaire, at weeks 2, 6, and 10 in person, via telephone or electronic media.
- 3.4.4 Blood samples for CBC with differential, platelet count, and PT/PTT/INR, serum and plasma banking, and optional CTC (if patient agrees) assessment will be collected prior to treatment and at weeks 2, 6 and 10.
- 3.4.5 Tests to measure serum electrolytes, BUN, creatinine, glucose, albumin, alkaline phosphatase, AST or ALT, LDH, total bilirubin, amylase, lipase, magnesium and ionized calcium will be performed at weeks 2, 6, and 10.
- 3.4.6 Optional urine (if patient agrees) will be collected prior to treatment and at weeks 2, 6 and 10.
- 3.4.7 Chest x-ray will be performed immediately after catheter placement and at weeks 2, 6, and 10.

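### Serum is named as the blood matrix for H3/H4 acetylation, but serum holds no cells and no blood-cell sample is assigned to the assay; the effusion part names no tumour-cell gate

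*Combined protocol and SAP*

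**What the plan says.** Two places name the specimens for histone acetylation. Objective 2.3.2 lists it, after cytokines on the Luminex platform, as "the degree of H3 and H4 hyperacetylation in serum and pleural effusion cells". The fourth aim in section 2.1 gives the time points: "H3 and h4 hyperacetylation and inflammatory cytokines in the effusion and in the serum at baseline and at week 2".

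The research blood is described in section 3.4.4: "serum and plasma banking, and optional CTC (if patient agrees) assessment will be collected prior to treatment and at weeks 2, 6 and 10". The Study Parameters table lists optional blood without saying which fraction is kept. Section 6 (Translational Studies) makes the CTC work depend on funding.

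The reason for the measurement is in section 1.0: "Serial fluid samples will be examined to validate the translational hypothesis and ensure HDAC inhibition occurs".

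On what was measured before, section 1.1 says of the phase I/II study of valproic acid with epirubicin or FEC100 that "histone acetylation and topo II expression were evaluated in pre-and post-VPA peripheral blood mononuclear cells and tumor samples". On the make-up of effusion fluid, section 1.1 reports from the sponsor's own 29-patient series: "Median percentage of CD45-CD326+ cells was 1.24% which contained a median TIC component of 9.5" per cent.

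**The concern.** An HDAC inhibitor acts on histones in the nuclei of cells. A serum tube has had its cells removed, so the plan sends the blood part of this objective to a specimen that does not contain the target. If the cell layer is discarded at baseline and week 2, it cannot be recovered later, so the matter has to be settled before sampling.

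The effusion part raises a separate question of interpretation. The hypothesis in sections 1.1 and 1.3 concerns tumour cells. The acetylation objective refers to effusion cells in general, whereas the stem-cell-marker objective in the same list refers to tumour cells in the effusion. If the assay were run on all cells together, a change or its absence could not be assigned to tumour cells.

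At stake is how a null clinical result could be explained. Routine drug levels would not fill the gap. Section 5.2 and the schedule footnote call for serum valproate where indicated or after grade 2 or higher adverse events, and a level measures exposure, not HDAC inhibition.

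**Working it through.** No figure in the plan can be reproduced here. The 1.24% is a laboratory median reported without raw data, and no sample size or power is given for acetylation. The check sets the sections side by side and adds one illustration.

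**Blood part**

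| Source | Specimen for acetylation |
|---|---|
| Section 2.1, fourth aim | serum (and effusion) |
| Section 2.3.2 | serum (and effusion cells) |
| Section 1.1, epirubicin/FEC100 study | mononuclear cells and tumour |
| Section 1.2.1, cervical cancer phase I study | tumour, and peripheral blood in the 4 patients who could be evaluated |
| Section 1.2.1, intravenous phase I study | peripheral blood by western blot, raised in 12 of 16 patients |

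No cited study is described as using serum. Section 3.4.4 then gives the blood collected: clinical tests, banked serum, banked plasma, and an optional CTC sample. The blood-count tube and any CTC tube do contain cells, but neither is assigned to histone work. The most that could be measured is 76 patients × 2 time points = 152 blood readings. As written, the serum and plasma tubes give 0 cellular readings. If a cell-free histone assay was meant, the protocol neither names one nor cites a precedent.

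**Effusion part**

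- Section 3.4.9 collects effusion at each clinic visit, and section 3.1 says correlates are run on fresh samples.
- Section 6 plans flow cytometry with CD45-EpCAM+ gating for cell cycle and stem-cell markers. It does not mention H3 or H4 and gives no analysis for them.
- So suitable cells and a suitable gate exist, but the plan does not connect them to acetylation.

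**How much the gate could matter (illustration).** Let *f* be the epithelial fraction and *k* the fold rise in acetylation in epithelial cells. Assume equal histone per cell. If only epithelial cells respond:

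ungated signal relative to baseline = (1 − *f*) + *f* × *k*

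With *k* = 3:

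| *f* | Calculation | Ungated signal |
|---|---|---|
| 1.24% (sponsor's series) | 0.9876 + 0.0124 × 3 | 1.025 |
| 5% (assumed) | 0.95 + 0.05 × 3 | 1.10 |
| 10% (assumed) | 0.90 + 0.10 × 3 | 1.20 |
| 25% (assumed) | 0.75 + 0.25 × 3 | 1.50 |
| 50% (assumed) | 0.50 + 0.50 × 3 | 2.00 |

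If every cell type responds equally, the ungated signal is *k* itself, here 3.00, whatever *f* is. The result therefore depends on two things the plan does not fix: the epithelial fraction in trial patients, and whether non-tumour cells respond. In neither case does an ungated value identify which cells responded.

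**The case against.** **The sentences might be read item by item.** In 2.3.2 the order is cytokines then acetylation, with serum then effusion cells. In 2.1 both pairs are reversed. One could pair cytokines with serum and acetylation with effusion throughout. Neither sentence says so, and the ordinary reading gives both assays both specimens. If the narrower pairing was meant, the plan has no blood acetylation measure, and restricting serum to cytokines is still the right edit.

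**Section 3.4.4 may not list all sample processing.** That is fair. A cell layer might be kept under a laboratory procedure, but nothing in the plan assigns one to this assay.

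**Proof of HDAC inhibition rests on fluid.** This stands. Section 1.0 speaks of serial fluid samples, so a faulty blood part does not remove the stated proof. A reader might infer that the trial loses its only pharmacodynamic evidence, but the documents do not support that. Section 6 also plans a downstream measure, the percentage of quiescent epithelial cells and its change from baseline, in both arms.

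**Nothing says the effusion assay is ungated.** This also stands. A reader might infer that the planned samples cannot show HDAC inhibition in tumour cells. They can, since fresh effusion cells are collected and the gate is already in use for other markers. What is missing is the specification.

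**The 1.24% may not carry over.** The series was of unselected patients, and inclusion criterion 4.1.7 requires positive cytology. No spread is given. Neither this fraction nor a dilution figure based on it should be quoted as the size of the problem in this trial.

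**Non-tumour cells are informative too.** The cited studies report blood-cell or peripheral-blood acetylation that correlated with tumour. Acetylation in non-tumour effusion cells would likewise show drug action in the pleural space. This is a reason to label such a result correctly, and it also means that a mononuclear-cell result would be a systemic marker, not tumour evidence.

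**Conclusion.** The blood part of objective 2.3.2 cannot, as written, give the cellular acetylation readout used in the studies the protocol relies on. It names a cell-free specimen, and no blood cells are assigned to the assay. The loss is all of up to 152 blood readings. This rests on the ordinary reading of sections 2.1 and 2.3.2, and on 3.4.4 being a complete statement of the research blood.

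The effusion part is a gap in specification. A tumour-cell readout is obtainable from the planned samples if a gate is written in. Without one, a result describes the pleural compartment and cannot be attributed to tumour cells. The size of that ambiguity in this trial is unknown.

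The point concerns one secondary, correlative objective. It does not touch the primary endpoint, the randomisation or the safety monitoring. It should be corrected before samples are taken, because unretained cells cannot be replaced.

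**What to change.** - In sections 2.1, 2.3.2 and 3.4.4, limit serum to the cytokine assay.
- In 3.4.4, keep a mononuclear-cell pellet or lysate from the research blood already drawn at baseline and week 2, and name it as the blood specimen for H3/H4 acetylation.
- In 2.3.2 and Section 6, state that effusion acetylation is reported within the CD45-EpCAM+ gate already planned, where cell yield allows.
- Where yield does not allow it, report the ungated value, label it a pleural-compartment marker, and do not attribute it to tumour cells.

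The cost is wording in four places, processing of blood already drawn, and the work of adding acetylation to an existing flow panel. No extra visit or patient procedure is needed. The practical limit is gated-cell yield: Section 6 already divides its flow samples into three replicates, and a low epithelial fraction would leave few cells per replicate.
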